Using a large sample, we will determine the psychometric properties of health questionnaires across levels of health literacy. Testing will be conducted in English and Spanish, across two modes of administration (paper-and-pencil vs. talking touchscreen). Each participant will have three visits (baseline, 3-month, and 6-month follow-up), described below, in order to determine changes in psychometric properties over time. We will use *differential item functioning* (DIF) and other psychometric analyses to identify questionnaire items with varying characteristics across levels of health literacy. Before the COVID-19 pandemic, our original plan was to recruit $N = 1216$ participants for in-person assessments. At the time of this plan our final N is 728 participants who have completed a health literacy assessment; some of these participants are missing data on subsequent questionnaires. In-person recruitment was put on hold during the COVID-19 pandemic; in order to adapt the the pandemic, a subset of participants ($N = 304$) was invited to a phone-based protocol that included data collection about the impact of COVID-19, vaccine confidence, and health-related quality-of-life (PROMIS-29 profile).

- **Develop alternative modes of test administration that can better accommodate people with low health literacy.** National statistics indicate that 14% of adults in the United States have below basic reading skills, and over 75 million Americans have below basic or basic health literacy skills.¹⁴ These data strongly indicate that many individuals seeking health care will have difficulties with written questionnaires, even those that have been carefully developed such as those in the NIH PROMIS. We will test an alternative mode of administration that has been specifically designed to aid people of low health literacy – a computer-assisted “talking” version that uses speech technology that participants can privately access as needed to have items and response options

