Data will be summarized by group and in total. In summary tables of continuous variables, the minimum, maximum, mean, and standard deviation will be presented with one decimal place. We will use counts and percentages in table for categorical variables. The denominator for each percentage will be the number of participants within the group unless otherwise specified. All hypothesis testing will be carried out at a two-tailed Type I error rate of $\alpha = .05$ unless otherwise specified. P-values will be rounded to three decimal places with a minimum of < 0.001 in tables. If statistical methods change during analysis, this will be documented in all reports with justification. Additional analyses of these data will be inevitable, but any exploratory analyses will be clearly marked as such.

Statistical power analysis and sample size selection

IRT and DIF analyses require large samples due to the large number of free parameters to be estimated. The proposed sample size herein is larger than other successful implementations of these same analyses carried out in other IRT studies.¹⁶⁻¹⁹ Moreover, we have carried out computer simulations to determine if our proposed sample sizes will be sufficient to create IRT models. We assumed a one-factor model across two groups at $n = 100$ each with standardized factor loadings set to .7 for eight questionnaire items. We used two groups for this simulation to ensure that any pairwise model comparisons would have adequate power. For this simulation, we specified that a non-significant model χ^2 was a good fit, which is a conservative decision because this particular test is highly sensitive relative to other measures of model fit, especially with large samples. Across 500 iterations, a good-fitting model was identified across groups 90% of the time. Even dropping the sample size to as low as $n = 50$ would identify a good-fitting model 84% of the time.

Missing data

We will describe the rate of missing data on an item-by-item basis using frequency tables in R. We do not anticipate high rates of missing data, but we will conduct subgroup analyses by health literacy, site, and administration mode as need to help diagnose any problems with missing data. For DIF analyses, IRT models

Table 1	
Visit 1 (Baseline)	Description of instrument
Language Assessment	To determine testing in English or Spanish
Single Item Health Literacy Screener	To screen for possible literacy status

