PROMIS Profile	To assess health-related quality of life.
PHQ-9	Self-report measure of depression.
Berlin Questionnaire (for sleep)	Self-report measure of sleep quality.
Purpose and Meaning (NIH Toolbox)	Self-report measure of the degree of meaning and purpose a person feels in their life.
RRS	Self-report measure of negative, repetitive thoughts.
PTSD Checklist	Self-report measure of posttraumatic stress disorder symptoms.
*C-SSRS Lifetime	Self-report measure of recent history of suicidal ideation and behavior. (This is not a variable of interest that will be used only to ensure patients' safety).
*C-SSRS Last Contact	Self-report measure of suicidal ideation and behavior since the individual's most recent assessment. (Used only as necessary to ensure patients' safety).
Exit Interview	

are estimated using full-information approaches that use all available data and can accommodate missing responses. We do not foresee a need for an imputation strategy, but if that were to become necessary, we will update this plan accordingly before running any analyses.

Study Design

This is a randomized experiment aimed at determining whether talking touchscreen technology can reduce DIF and provide a better testing experience, relative to paper-based testing. The original study design is shown below in Table 2, although as a result of the COVID-19 pandemic, we were unable to recruit all 1216 participants, but instead collected additional longitudinal data on a subset of participants ($n = 304$)

Table 2: Study Design			
Northwestern		BUMC	

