304 English speaking 152 with low health literacy 76 women g1 38 randomized to paper-based 19 Order 1 19 Order 2 38 randomized to talking touchscreen 19 Order 1 19 Order 2 76 men g2 38 randomized to paper-based 19 Order 1 19 Order 2 38 randomized to talking touchscreen 19 Order 1 19 Order 2 152 with adequate health literacy 76 women g3 38 randomized to paper-based 19 Order 1 19 Order 2 38 randomized talking touchscreen 19 Order 1 19 Order 2 76 men g4 38 randomized to paper-based 19 Order 1 19 Order 2 38 randomized talking touchscreen 19 Order 1 19 Order 2	304 Spanish speaking 152 with low health literacy 76 women g5 38 randomized to paper-based 19 Order 1 19 Order 2 38 randomized to talking touchscreen 19 Order 1 19 Order 2 76 men g6 38 randomized to paper-based 19 Order 1 19 Order 2 38 randomized to talking touchscreen 19 Order 1 19 Order 2 152 with adequate health literacy 76 women g7 38 randomized to paper-based 19 Order 1 19 Order 2 38 randomized talking touchscreen 19 Order 1 19 Order 2 76 men g8 38 randomized to paper-based 19 Order 1 19 Order 2 38 randomized talking touchscreen 19 Order 1 19 Order 2	304 English speaking 152 with low health literacy 76 women g9 38 randomized to paper-based 19 Order 1 19 Order 2 38 randomized to talking touchscreen 19 Order 1 19 Order 2 76 men g10 38 randomized to paper-based 19 Order 1 19 Order 2 38 randomized to talking touchscreen 19 Order 1 19 Order 2 152 with adequate health literacy 76 women g11 38 randomized to paper-based 19 Order 1 19 Order 2 38 randomized to talking touchscreen 19 Order 1 19 Order 2 76 men g12 38 randomized to paper-based 19 Order 1 19 Order 2 38 randomized to talking touchscreen 19 Order 1 19 Order 2	304 Spanish speaking 152 with low health literacy 76 women g13 38 randomized to paper-based 19 Order 1 19 Order 2 38 randomized to talking touchscreen 19 Order 1 19 Order 2 76 men g14 38 randomized to paper-based 19 Order 1 19 Order 2 38 randomized to talking touchscreen 19 Order 1 19 Order 2 152 with adequate health literacy 76 women g15 38 randomized to paper-based 19 Order 1 19 Order 2 38 randomized to talking touchscreen 19 Order 1 19 Order 2 76 men g16 38 randomized to paper-based 19 Order 1 19 Order 2 38 randomized to talking touchscreen 19 Order 1 19 Order 2

Study Timepoints

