Our exit interview serves multiple purposes. One purpose is to assess the testing experience for the participant. We hypothesize differences between the talking touchscreen and paper-based testing in terms of the testing experience. We will calculate Spearman correlations with 99% confidence intervals (CIs) for the three 5-point ordinal questions (see Exit Interview) and whether testing was talking touchscreen or not (coded 0/1). This nonparametric approach will determine which method of testing is more appropriate for people of low health literacy. CIs that do not contain zero will be regarded as statistically significant.

A second purpose of the exit interview is to gather data on how health literacy influences other areas of health. Specifically, we have included four questions about colorectal cancer screening to determine a person's level of adherence to published guidelines.

Meaning and purpose in life, defined as the pursuit of worthwhile goals and an accompanying sense of fulfillment and coherence in one's life,²⁶⁻³⁰ is recognized as a fundamental facet of psychological wellbeing and important determinant of both physical and mental health. Individuals who report greater meaning and purpose are more motivated to engage in their healthcare and improve their overall health and wellbeing. Research demonstrates that individuals who report greater meaning and purpose also endorse greater self-efficacy, or perceived confidence in the ability to manage one's health, and are more likely to participate in preventive health services, including cholesterol screenings, colonoscopies, mammograms, Pap smears, and prostate exams.³¹⁻³³ In the current study, we will examine the impact of meaning and purpose in life and health-related quality of life (i.e., anxiety, depression, fatigue, pain intensity and interference, physical function, sleep disturbance, and disruption of social roles and activities) on adherence to national guidelines for colorectal cancer screening. Colorectal cancer screening was assessed using the National Cancer Institute Health Interview National Trends Survey (HINTS).³⁴ Adherence will be defined as receipt of screening within recommended timeframes according

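### The exit-interview comparison of touchscreen and paper ignores the factors used to allocate mode, and loses precision to the extent that those factors predict the ratings

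*SAP*

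**What the plan says.** The Exit Interview section of the SAP plans "Spearman correlations with 99% confidence intervals (CIs) for the three 5-point ordinal questions", each correlated with "whether testing was talking touchscreen or not (coded 0/1"). The decision rule is "CIs that do not contain zero will be regarded as statistically significant", which amounts to a two-sided level of .01 per rating. No site, language, literacy or gender term appears, and no other section supplies one for this comparison.

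Table 2 (SAP, Study Design) lays out 16 groups, g1 to g16, defined by site, language, literacy and gender. The first reads "76 women g1 38 randomized to paper-based 19 Order 1 19 Order 2 38 randomized to talking touchscreen", and the others follow the same pattern. The text introducing the table presents it as the design before the pandemic and adds that "we were unable to recruit all 1216 participants". The Study Objectives section gives a final N of 728 with a completed literacy assessment. Neither document describes a blocking scheme, and neither states the number of completed exit interviews.

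**The concern.** Testing experience is one of the two aims that the SAP's Study Design section gives for randomising mode, and this is the only planned test of it. When allocation is balanced inside groups that predict the outcome, differences between groups cannot contribute to the mode contrast. A two-variable correlation nevertheless leaves that variation in its error term. The interval is then wider than the data require, and a real difference in experience is more likely to be missed. That matters more in a sample smaller than planned and judged at the 99% level.

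The SAP respects design factors elsewhere. The primary DIF analyses and the longitudinal factor models are run within language and within mode. This comparison uses none of the factors.

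**Working it through.** **The plan's own figure.** 2 sites × 2 languages × 2 literacy levels × 2 genders = 16 groups, and 16 × 76 = 1216, which is the planned total. So 38:38 inside each group is the layout behind the planned N.

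**Inputs.** The level is two-sided .01, so z = 2.576. N is at most 728; the exit-interview N will be lower because that interview takes place at the last visit. R², the share of rank variance explained by the groups, is not in the documents, so 0 to .30 is assumed.

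**Balanced allocation inside groups.**
- Planned half-width near zero correlation: 2.576/√(N−3). At 728 this is 2.576/√725 = .0957; at 1216 it is .0740.
- Half-width when the groups are accounted for, on the same scale: .0957 × √(1−R²).
- Excess width: 1/√(1−R²) − 1, which does not depend on N.
- Actual null rejection rate of the planned test: 2[1 − Φ(2.576/√(1−R²))].
- Equivalent extra participants: 728/(1−R²) − 728.
- Power for a correlation of .10 (assumed). Planned: 1 − Φ((2.576 − .10√728)/√(1−R²)). Adjusted: 1 − Φ(2.576 − .10√728/√(1−R²)).

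| R² (assumed) | Adjusted half-width | Planned interval wider by | Null rejection, planned | Extra participants | Power, planned / adjusted |
|---|---|---|---|---|---|
| 0 | .0957 | 0% | .0100 | 0 | .55 / .55 |
| .05 | .0932 | 2.6% | .0082 | 38 | .55 / .58 |
| .10 | .0908 | 5.4% | .0066 | 81 | .55 / .61 |
| .20 | .0856 | 11.8% | .0040 | 182 | .55 / .67 |
| .30 | .0800 | 19.5% | .0021 | 312 | .56 / .74 |

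A simulation agrees (16 groups of 46, N = 736, five-category ratings, balanced allocation, 4000 runs). At a rank R² of about .24, the standard deviation of the correlation was .0324 against the .0369 that the interval uses. The ratio is .88, and √.76 = .87. Null rejection was .0043 planned and .0097 adjusted. With a latent mode shift of .2 SD, power was .48 and .62.

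**Simple 1:1 allocation, not balanced inside groups.** Under no mode effect the rank correlation then has variance 1/(N−1), whatever the groups explain. At N = 480 (assumed) this gives 1/√479 = .0457, against 1/√477 = .0458 in the interval. A 4000-run simulation with 16 groups of 30 gave standard errors of .046 and .047 and coverage of 98.9% and 98.7% at R² of .20 and .30. The Monte Carlo error is √(.99 × .01/4000) = .0016, so both values lie within two standard errors of 99%. Adjustment still helps. With a latent shift of .25 SD, simulated power was .51 against .54, .50 against .60 and .51 against .65 at R² of .10, .20 and .30.

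**Cost of adjusting when R² = 0.** Four main effects change √725 to √721, a widening of √(725/721) − 1 = 0.3%. Fifteen group terms give √(725/710) − 1 = 1.1%.

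**Cell sizes.** The Meaning and Purpose section gives 566 English speakers at baseline. If they are among the 728, at most 728 − 566 = 162 are Spanish speakers. That is about 162/8 = 20 per Spanish cell, against at least 566/8 = 71 per English cell.

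**The case against.** A reader might infer that the 99% interval is too wide as a matter of fact and covers more than 99%. The documents do not support that. It needs allocation balanced inside the groups and groups that predict the ratings. Table 2 is a planned layout that was not filled, no blocking is described, and no R² is given. Under simple allocation the coverage is correct. This limits the claim but does not remove it, because adjustment gains power under either form of allocation.

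A reader might also infer a validity problem. There is none: the per-rating error stays at or below .01.

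The size may be small. Nothing in the documents shows that these factors explain 20% to 30% of the variance of a single five-point item; at 10% or less the excess width is about 5% or less. The 99% level itself costs more (2.576/1.960 = 1.31, or 31% wider than 95%), but that level is a stated choice, whereas no reason is given for leaving out the allocation factors. An R² of exactly zero would also sit oddly with the study's premise that literacy affects how people manage written questionnaires.

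Two further objections stand and shape the fix. First, the SAP's opening section says that screening data were explored to improve stratification, so the strata used for allocation may differ from the Health LiTT groups. Second, a proportional-odds model would add an assumption to a deliberately nonparametric analysis.

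**Conclusion.** The comparison omits the factors within which Table 2 allocates mode, and it loses precision to the extent that they predict the ratings. The loss runs from nil at R² = 0 to about 5% of interval width at .10 and 20% at .30, if allocation was balanced inside the groups. Otherwise the interval is correctly calibrated and the loss appears only as lower power than an adjusted analysis would have. The R² values, the use of 728 as an upper limit for N, and the correlation of .10 are assumptions; the omission and its direction are not. This is a point about efficiency, not validity. It is worth acting on because the change costs almost nothing even when the factors explain nothing. It concerns the precision of the overall comparison; whether a comparison pooled over literacy groups can speak for people with low literacy is a separate question.

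**What to change.** Make the main analysis of each rating a rank-based one that accounts for the allocation factors, using the strata as actually used at randomisation. One form is a partial Spearman correlation of rating with mode, adjusted for site, language, literacy group and gender, with its 99% interval and the existing decision rule. The partial correlation is scaled to the variation left after adjustment. The gain therefore shows mainly as an estimate further from zero relative to its standard error, and its printed width should not be compared directly with that of the unadjusted correlation. A van Elteren test is the alternative if a stratified test is preferred.

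Enter the factors as main effects or merge sparse cells by a rule set in advance, since Spanish-language cells may be small. State how mode was allocated and how many exit interviews are available. Keep the unadjusted Spearman correlation as description. A proportional-odds model is optional, with the small downside of a proportionality assumption and a conditional odds-ratio scale.

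The cost is a few sentences in the SAP and one extra analysis step per rating. No new data are needed.

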At the end of the study, a research assistant will also debrief the participant about the purpose of the study, and conduct an exit interview to determine how comfortable the participant felt answering the questions and to learn what did and did not work well. As part of the exit interview, for participants that are 45 years of age or older, we will ask a short battery of questions about colon cancer screening and then all participants will be presented with a small set of questions to get detailed feedback from individuals on how they understood certain questions, what type of response format they prefer, and what was or was not confusing. These colon cancer screening questions relate to the Meaning and Purpose questionnaire that is already embedded in our study as individuals who report greater meaning and purpose are more motivated to engage in their healthcare and improve their overall health and wellbeing and are more likely to participant in preventive health services,

including colonoscopies, etc. Based on screening recommendations from the American Cancer Society, we will be asking these additional questions to participants that are 45 years of age or older to determine if participants are adherent to the recommended screening timeframes. According to the guidelines from the United States Preventive Services Task Force and the American Cancer Society. Participants are classified as adherent if they reported receipt of either a FOBT within 1 year, colonoscopy within 10 years, sigmoidoscopy within 5 years, or both a colonoscopy and sigmoidoscopy within 10 years. We will then relate participant's adherence to their answers to the Meaning and Purpose questionnaire.

Research procedures and activities for phone-based protocol:

Due to the COVID-19 pandemic, the study will implement phone-based assessments in addition to the original in-person protocol. A research team member will contact enrolled or previously enrolled participants to give more information about the phone-based protocol and to assess interest. If a participant is interested, they will be verbally consented over the phone. Each of the three phone sessions will last approximately 60 minutes. At each phone-based visit, the participant will respond to the following questionnaires via phone-based administration:

- 1. PROMIS-29
- 2. NIH Toolbox Meaning and Purpose
- 3. Colorectal Cancer Screening Questions (at one time-point, if not already completed at an in-person visit)

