read to them. We will analyze the talking touchscreen groups and paper-based groups separately. We hypothesize that the talking touchscreen will reduce health literacy-related test bias by level of health literacy, relative to traditional paper-based methods. This will be evidenced by fewer items being flagged for DIF in the group that receives the talking touchscreen. In terms of descriptive statistics to display the magnitude of effects, we will report effect sizes (McFadden's R^2) of DIF items, as well as test characteristic curves (TCCs) for DIF items. Among participants with low health literacy, we expect that the discrimination parameters of the touchscreen condition will be higher than the paper-based condition.

- **Determine the degree of differential item functioning (DIF) of tools relevant to clinical research across different levels of health literacy.** DIF analyses will be conducted to identify test bias by level of health literacy. This will ensure that individuals with low literacy are assessed fairly in clinical and research settings. We will assess a broadly applicable instrument to primary care – the PROMIS Profile, which measures anxiety, depression, fatigue, pain interference, pain intensity, physical function, sleep disturbance, and social roles and activities. Other questionnaires included in the study are shown in Table 1. We will stratify participants into low versus adequate literacy levels using Health LiTT (groups will be formed according to T scores of < 55 vs. 55+).¹⁵ A secondary analysis will use the NUMI, a measure of health numeracy, in three groups (low = 0-3, medium = 4-6, high = 7 or greater). Then, we will determine whether psychometric properties of each questionnaire scale are consistent for individuals with low health literacy versus adequate health literacy. We hypothesize that DIF will be observed for multiple scales using paper-and-pencil administration, suggesting a need to improve test items, and a need to examine alternative ways to administer these tools.

Statistical methodology

Overview

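### The exit-interview correlations state no health-literacy restriction, stratum or interaction, so they do not by themselves support the planned conclusion about people with low health literacy

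*SAP*

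**What the plan says.** The SAP's Exit Interview section opens with a general hypothesis: "We hypothesize differences between the talking touchscreen and paper-based testing in terms of the testing experience". The test is then set out: "We will calculate Spearman correlations with 99% confidence intervals (CIs) for the three 5-point ordinal questions". The other variable in each correlation is "whether testing was talking touchscreen or not (coded 0/1"). The decision rule is "CIs that do not contain zero will be regarded as statistically significant". The stated use of the result is "This nonparametric approach will determine which method of testing is more appropriate for people of low health literacy".

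The section names no analysis set, no literacy stratum and no interaction term for this test.

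The protocol (section 4.3) gives the interview at the end of the study to "conduct an exit interview to determine how comfortable the participant felt answering the questions and to learn what did and did not work well", with no limit by literacy. SAP Table 1 places it at Visit 3. The SAP's Study Objectives define the literacy groups from Health LiTT ("groups will be formed according to T scores of < 55 vs. 55" or above). Table 2 plans "152 with low health literacy" and 152 with adequate literacy in each site-by-language block of 304.

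**The concern.** The hypothesis and the calculation concern mode in general, but the conclusion concerns one literacy group. Without a literacy term, the correlation is a mixture of the mode effects in the low- and adequate-literacy groups.

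Two errors can follow:

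- A benefit confined to low-literacy participants is diluted and may be missed.
- A preference held only by adequate-literacy participants can produce an interval that excludes zero. Under the plan's rule it would then be reported as showing what suits people with low literacy.

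The touchscreen was designed with low-literacy users in mind, so an equal effect in both groups is not a safe default.

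**Working it through.** **Is a stratum implied elsewhere?** Where the SAP intends strata or moderators, it names them:

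- The DIF section runs separate analyses within language and format, across literacy groups.
- Study Timepoints sets out models by literacy group.
- The depression-prediction section uses Health LiTT as a moderator.
- The Meaning and Purpose section has a Health LiTT by administration-type interaction.

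The Exit Interview section has nothing comparable. The Overview's general line about summarising data by group and in total concerns summaries and does not define this test.

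**Is there a figure to reproduce?** No. The documents give no sample size, effect size or power for these correlations. The design counts do agree: 16 cells × 76 = 1216 planned, of which 8 × 76 = 608 have low literacy (50%).

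**Inputs**

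- Two-sided alpha .01, from the 99% CI (critical value 2.576).
- n = 728, the SAP's final number with a health literacy assessment. This is an upper bound, because the interview is at Visit 3.
- Low-literacy share 30%, 50% or 70% (n = 218, 364, 510). This is an assumption, because the achieved split is not given.
- r = .20 in one literacy group and zero in the other. This is an assumption.

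**Formula.** Power ≈ Φ(atanh(r) / √(1.06/(n − 3)) − 2.576). An effect r confined to a fraction p of the sample gives an overall correlation of about p × r.

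**Effect only in low literacy (r = .20)**

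| Low-literacy share | Overall r | Overall power, n = 728 | Subgroup n | Subgroup power |
|---|---|---|---|---|
| 30% | .06 | 16% | 218 | 62% |
| 50% | .10 | 52% | 364 | 88% |
| 70% | .14 | 87% | 510 | 97% |

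As a worked example, take the 50% row. Overall, atanh(.10)/√(1.06/725) = 2.62, and Φ(2.62 − 2.576) = 52%. In the subgroup, atanh(.20)/√(1.06/361) = 3.74, and Φ(3.74 − 2.576) = 88%. With 500 interviews and a 50% share (both assumed), the pair is 34% against 70%.

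**Effect only in adequate literacy (r = .20).** The overall correlation is .14 / .10 / .06 at low-literacy shares of 30% / 50% / 70%. The overall CI excludes zero 87% / 52% / 16% of the time, although the low-literacy effect is zero.

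**Equal effect in both groups (r = .15, 50% share).** Overall, atanh(.15)/√(1.06/725) = 3.95, giving 92%. In the subgroup of 364, atanh(.15)/√(1.06/361) = 2.79, giving 58%. Here the overall analysis estimates the right quantity and is more precise.

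**Check on 5-category data.** The 1.06 variance factor is an approximation for continuous data, so the pattern was also simulated with five-point responses (1000 runs per scenario, n = 728, 50% share, Fisher z intervals, assumed response cut-points):

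- A 0.5 SD effect in adequate literacy only gave an overall rho of 0.116. The overall interval lay above zero in 73% of runs, against 0.3% in the low-literacy group.
- Opposite effects of 0.4 SD, favouring the touchscreen in low literacy, gave an overall rho of about 0. The interval lay above zero in 0.7% of runs overall, against 84% in the low-literacy group.
- Equal effects of 0.4 SD gave rho of 0.185 overall and 0.186 in low literacy.

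**The case against.** The strongest reply is that the correlation matches the hypothesis it serves. That hypothesis is a mode difference with no literacy term, and mode is randomized, so the overall correlation tests it validly. Only one interpretive sentence goes further. This stands: a reader might infer that the overall correlation is unsound or should be reduced to description, and the documents do not support that.

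A second reply is that the SAP never says it will pool everyone. The only population the paragraph names is people with low literacy, so a filter may have been intended and left out. This also stands in part. Pooling is inferred from silence. But an intended filter that is not written down is still a gap in a plan meant to fix decisions in advance.

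Third, the magnitude depends on assumptions. Table 2's even split belongs to the 1216-person design, not to the 728 reached. The documents give neither the achieved split nor the number of exit interviews. This is why ranges are shown and one value of r is used for both one-group scenarios. It is also why the equal-effect case, which favours the overall analysis, is included.

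Finally, the DIF analyses address literacy and mode directly. That limits the importance of this point but does not supply evidence about testing experience in low-literacy participants.

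**Conclusion.** The mismatch between the analysis as written and its stated conclusion is clear from the Exit Interview section alone. The overall correlation answers whether testing experience differs by mode. It answers which mode suits people with low literacy only if the mode effect is the same in both literacy groups, and nothing planned for these ratings tests that.

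On the stated assumptions, an effect of r = .20 confined to adequate literacy would be declared overall between 16% and 87% of the time, depending on the literacy split. The same effect confined to low literacy would be missed between 13% and 84% of the time overall (100% minus the power of 87% and 16%), against 3% to 38% within the low-literacy group. These figures illustrate direction and rough size. They do not predict this trial's result, and with fewer than 728 interviews power falls.

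A reader might infer that the trial's main comparison of modes is compromised. It is not. This is a secondary analysis of testing experience, and the DIF analyses do not depend on it. The point is worth correcting before the exit-interview results are interpreted.

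**What to change.** In the SAP's Exit Interview section:

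1. State the analysis set. Keep the overall Spearman correlation with its 99% CI as the test of the mode-difference hypothesis.
2. Add the same correlation and 99% CI within Health LiTT T < 55, with the T ≥ 55 group shown beside it.
3. Base any statement about low-literacy participants only on the T < 55 estimate. A mode-by-literacy interaction in an ordinal model is optional.
4. If the authors do not want a low-literacy analysis, reword the concluding sentence so that it claims only an overall mode difference.

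No new data are needed: Health LiTT is collected at Visit 1 and the cut-off is already set. The cost is a wording change, one extra run by literacy group, and lower precision for the low-literacy estimate. If the effect is equal in both groups (r = .15, 728 interviews, half low literacy), power is 58% in the subgroup against 92% overall. A low-literacy interval that includes zero should therefore be reported as inconclusive, not as showing that the modes are equivalent.
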